13.1.2. Vital Signs

Vital signs (seated heart rate and blood pressure after at least 5 minutes of rest) will be recorded at Visit 1A (Screening) and, if applicable, Visit 1B (Re-screening); Visit 2 (Randomization); and all subsequent visits.

13.1.3. Weight and Height

Subject weight and height will be measured at Visit 1A (Screening) and, if applicable, Visit 1B (Re-screening). Weight will also be measured at Visit 2 (Randomization), Visit 9 (Week 24), Visit 12 (Week 48), and ET Visit.

13.1.4. Laboratory Assessments

All laboratory values for this study will be determined by a Sponsor-designated Central Laboratory. The Central Laboratory will provide all materials and procedures for the collection of laboratory samples to be sent to the Central Laboratory. Decisions regarding study drug dosing should be based on Central Laboratory test results only. If local laboratory tests are conducted as part of routine care and there are discrepancies between the Central Laboratory and local laboratory test results, the Investigator should use their clinical judgment and consult the Medical Monitor as needed.

Only Central Laboratory test results will be used for statistical analyses.

13.1.4.1. Hematology

A CBC (WBC count, WBC differential, RBC count, HCT, Hgb, RBC indices, platelet [thrombocyte] count) will be performed at Visit 1A (Screening) and, if applicable, Visit 1B (Re-screening); Visit 2 (Randomization); and all subsequent visits.

13.1.4.2. Blood Chemistry

A CCP (sodium, potassium, phosphorus, calcium, calcium [adjusted for albumin], chloride, carbon dioxide/bicarbonate, glucose, BUN, creatinine, eGFR, AST, ALT, ALP, total bilirubin, total protein, and albumin) will be performed at Visit 1A (Screening) and, if applicable, Visit 1B (Re-screening); Visit 2 (Randomization); and all subsequent visits

13.1.4.3. Iron Tests

Iron studies (TSAT, ferritin, UIBC, TIBC, and serum iron) will be performed at Visit 1 A (Screening) and, if applicable, Visit 1B (Re-screening); Visit 2 (Randomization); and all subsequent visits.

13.1.4.4. Other Tests

FGF23 (intact and C-terminal) will be performed at Visit 2 (Randomization), Visit 9 (Week 24), Visit 12 (Week 48), and the ET visit.

iPTH will be performed at Visit 1A (Screening) and, if applicable, Visit 1B (Re-Screening); Visit 2 (Randomization); Visit 9 (Week 24); Visit 12 (Week 48); and the ET visit.

13.1.4.5. Spot Urine Protein-to-Creatinine Ratio

Spot urine protein-to-creatinine ratio will be measured at Visit 2 (Randomization)

13.1.4.6. Frozen Serum Samples

For subjects that provide informed consent specifically for collection of serum samples for freezing, serum samples will be obtained at Visit 2 (Randomization), Visit 9 (Week 24), Visit 12 (Week 48), and the ET visit. The serum samples obtained will be frozen for future analysis of biomarkers of CKD. One candidate biomarker is Klotho for which efforts are underway to develop a better standard assay [Hu 2013]. Thus, the testing is deferred. The future analysis will only be for biomarkers of CKD such as Klotho, there will be no genetic testing done with the frozen specimens at any point.

13.1.4.7. Pregnancy Screen

Serum pregnancy test for all women of childbearing potential will be performed at Visit 1A (Screening) and, if applicable, Visit 1B (Re-screening). Post-menopausal women must be amenorrheic for at least 12 months to be considered of non-childbearing potential.

13.2. Adverse and Serious Adverse Events

13.2.1. Definition of Adverse Events

All AEs spontaneously reported by the subject and/or in response to an open question from the study personnel or revealed by observation, regardless of treatment group or suspected causal relationship to the study drug, will be recorded on the AE eCRF.

13.2.1.1. Adverse Event

An AE is any untoward medical occurrence in a subject or clinical study subject administered a medicinal (investigational) product and which does not necessarily have a causal relationship with the study treatment.

An AE can therefore be any unfavorable and unintended sign (eg, an abnormal laboratory finding), symptom, or disease temporally associated with the use of a medicinal product, whether or not considered related to the medicinal product. Any worsening of a pre-existing condition that is temporally associated with the use of the study drug (ie, occurs after the first dose of study drug) is also considered an AE and should be captured as “worsening” of the pre-existing condition.

13.2.1.2. Serious Adverse Event

The definitions and reporting requirements to which full adherence will be ensured during the conduct of the study are: 1) ICH Guidelines for Clinical Safety Data Management, Definitions and Standards for Expedited Reporting Topic E2A; 2) Code of Federal Regulations 312.12 IND Safety Reporting.

The Investigator or the Sponsor may determine the seriousness of an AE based on the criteria below.

An AE is considered **serious** if at least one of the following conditions apply:

- **Death**: An AE that results in the death of a subject. The cause of death or AE that resulted in a fatal outcome should be recorded and reported as the SAE
- **Life-threatening**: An AE that places the subject in the view of the Investigator or the Sponsor, at immediate risk of death from the event as it occurred (ie, this does not include an event that, had it occurred in a more severe form, might have caused death).
- **Disability/Incapacity**: An AE that results in a persistent or significant disability/incapacity or substantial disruption of the subject's ability to conduct normal life functions.
- **Hospitalization/Prolongation of Hospitalization**: An AE that results in subject hospitalization or prolongation of an existing hospitalization. Hospitalization refers to admission of a subject to a hospital for any length of time.

The following instances do not constitute hospitalization for the purposes of SAE reporting:

- Routine treatment or monitoring of the studied indication, not associated with any worsening in the baseline condition
- Elective or pre-planned treatment for a pre-existing condition that is unrelated to the indication under study and has not worsened since signing of the informed consent
- Treatment on an emergency outpatient basis for an event not fulfilling any of the definitions of an SAE given above and not resulting in a hospital admission for patient care
- Social reasons and respite care in the absence of any worsening in the patient's baseline condition
- **Congenital anomaly/birth defect**: A fixed, permanent impairment established at or before birth in the offspring of a study subject
- **Important Medical Event**: Medical and scientific judgment should be exercised in determining whether an event is an important medical/medically significant event. An important medical event may not result in death, be life-threatening, or require hospitalization. However, if it is determined that the event may jeopardize the subject and/or may require intervention to prevent one of the other outcomes listed in the

SAE definition provided above, the important medical event should be reported as serious/SAE. Examples of such events are intensive treatment in an emergency room for allergic bronchospasm, blood dyscrasias, or convulsions that do not result in hospitalization

13.2.2. Recording Adverse Events/Serious Adverse Events

All AEs/SAEs will be collected for all randomized subjects from the date informed consent was signed to completion of the study or to the last administration of study drug or the Investigator/subject decision to discontinue treatment, whichever occurs later. Subjects will be followed for a 28-day follow-up period that begins with completion of the study or after the last administration of study drug, or after the Investigator/subject decision to discontinue treatment, whichever occurs later.

An SAE that occurs during the 28-day follow-up period must be collected regardless of relationship to study drug.

Any SAE reported to the Investigator following completion of the 28-day follow-up period must be promptly reported to the study's Sponsor if it is considered "related" by the Investigator.

The AE term should be reported in standard medical terminology when possible. For each AE, the Investigator will evaluate and report the following:

- Seriousness
- Relationship to study drug
- Action taken with the study drug
- Onset date
- Ongoing or resolution date
- Outcome
- Intensity (if applicable)

For all AEs, the Investigator must pursue and obtain information adequate to determine the outcome of the AE and to assess whether it meets the criteria for classification as an SAE ([Section 13.2.1.2](#)) requiring immediate action.

Changes in laboratory values, blood pressure, and pulse need not be reported as AEs. However abnormal values that are deemed clinically significant, lead to discontinuation of administration of study drug, or constitute an SAE must be reported and recorded as an AE.

13.2.2.1. Intensity

Intensity will be assessed according to the following scale:

- Mild (awareness of sign or symptom, but easily tolerated)
- Moderate (discomfort sufficient to cause interference with normal day-to-day activities)
- Severe (incapacitating, with inability to perform normal day-to-day activities)

It is important to distinguish between serious and severe AEs. Severity is a measure of intensity whereas seriousness is defined by the criteria under [Section 13.2.1.2](#). An AE of severe intensity may not be considered serious if it does not meet any of the seriousness criteria listed in Section 13.2.1.2.

13.2.2.2. Relationship to Study Drug

An Investigator who is licensed in medicine must make the determination of causal relationship to the study drug for each AE.

The Investigator should use his/her knowledge of the patient, the circumstances surrounding the event, and an evaluation of any potential alternative causes to determine whether an AE is considered unrelated or related to study drug.

The following factors should be taken into consideration for determination of relationship to study drug:

- Temporal relationship of event onset to the initiation of study drug
- Course of the event, considering the effects of dose reduction
- The effects of study drug discontinuation or re-introduction (if applicable)
- Known association of the AE to ferric citrate therapy or with similar treatments
- Known association of the AE with the disease under study
- Presence of risk factors for the AE in the subject or use of concomitant medications known to be associated with the AE
- Presence of non-treatment-related factors that are anticipated or known to be associated with the occurrence of the AE (eg, conditions associated with the progress of the underlying disease)

Unrelated: The AE is considered “unrelated” to ferric citrate (study drug) if:

- there is evidence that clearly indicates an alternative explanation,
- the subject has not received study drug,
- the timing of the exposure to study drug and the onset of the AE are not reasonably associated in time, or
- other facts, evidence or arguments exist that suggest an alternative cause or explanation

Related: The AE is considered “related” to ferric citrate (study drug) if:

- administration of study drug and the AE are considered reasonably associated in time,
- the AE could be explained by exposure to study drug or by other causes, or no alternative has been identified,

- there is biological plausibility for the causal relationship between the AE and the study drug, and
- there is no alternative cause identified for the AE to occur.

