13.2.3. Reporting of Serious Adverse Events

All SAEs must be reported on the AE eCRF to the study Sponsor within 24 hours of becoming aware of the SAE.

The Sponsor will notify all Investigators of all reportable SAEs that are unexpected per Investigator's Brochure and considered related to the study drug. This notification will be in the form of an expedited safety report. Upon receiving such notices, the Investigator must review and retain the notice with other study-related documentation.

For all SAEs, the Investigator is obligated to pursue and provide information to the study Sponsor. In addition, the Investigator may be requested by the study Sponsor to obtain specific information in an expedited manner. This information may be more detailed than that captured on the AE eCRF. In general, this will include a description of the AE in sufficient detail to allow for a complete medical assessment of the case and independent determination of possible causal relationship. Information on other possible causes such as concomitant medications and concurrent illnesses must be provided as applicable.

The Investigator, Sponsor, and Institutional Review Board (IRB) will determine if the informed consent requires revision. The Investigator will comply with the IRB or the Independent Ethics Committee (IEC) procedures for reporting any other safety information.

Suspected serious adverse reactions and other significant safety issues reported from the study shall be reported to the relevant regulatory authorities by the study Sponsor in full adherence to the guidelines and regulations.

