Severity (Intensity on the eCRF) is classified as mild, moderate or severe where these categories denote increasing intensity, respectively. TEAEs starting after the first dose of study drug with a missing intensity will be classified as severe. If a subject has more than one TEAE within the same SOC/ PT, the AE with the worst case intensity will be used in the corresponding intensity summaries.

The only relationships of AE to study drug used in this study are “unrelated” and “related”. An AE’s relationship to study drug is based on the Investigator’s assessment. TEAEs with the relationship to study drug missing will be classified as “related” to study drug. If a subject has more than one AE within the same SOC and PT, the AE with the worst case relationship to study drug will be used in the corresponding relationship summaries.

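### The *related* definition for adverse events withdraws its own allowance for other causes, so a plausible drug reaction with an identified alternative must be rated *unrelated*

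*Protocol*

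**What the plan says.** Protocol 13.2.2.2 asks a medically licensed investigator to weigh seven factors and then rate each adverse event as *related* or *unrelated*.

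*Related* has four criteria:
1. Drug administration and the event are reasonably associated in time.
2. "the AE could be explained by exposure to study drug or by other causes, or no alternative has been identified".
3. "there is biological plausibility for the causal relationship between the AE and the study drug, and"
4. "there is no alternative cause identified for the AE to occur".

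The *and* that closes criterion 3 makes the list cumulative.

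*Unrelated* also has four criteria: evidence that clearly points to another explanation; no study drug received; timing not reasonably associated; and "other facts, evidence or arguments exist that suggest an alternative cause or explanation". The third ends in *or* ("the timing of the exposure to study drug and the onset of the AE are not reasonably associated in time, or"), so any one is enough.

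SAP 9.2.1 leaves no middle category: "The only relationships of AE to study drug used in this study are" *unrelated* and *related*. It adds that an event's "relationship to study drug is based on the Investigator’s assessment". A missing relationship is counted as *related*.

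**The concern.** Criterion 2 of *related* is written for the common case in which the drug is a credible cause but not the only one. Criterion 4 then shuts that case out. In a population with chronic kidney disease and concomitant medication, competing explanations are to be expected; the protocol's own list of factors tells the investigator to look for both.

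Several things depend on the rating:
- the tables of treatment-emergent events by relationship, by starting dose and by dosing sequence (SAP 9.2.1, items 3 and 4);
- reporting of SAEs that come to light after the 28-day follow-up, which is required only if the investigator considers them related (Protocol 13.2.2), and their further follow-up (Protocol 13.2.2.3);
- follow-up to resolution of non-serious events, which 13.2.2.3 requires only for related ones;
- possibly, notification of other investigators about SAEs that are "unexpected per Investigator's Brochure and considered related to the study drug" (Protocol 13.2.3).

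The SAP also drops tables and listings of medical history (7.4) and of concomitant medication (7.5). A reader of the report would have little means of seeing which *unrelated* ratings rested on an alternative cause.

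**Working it through.** The plan states no figure on this point, so the check is one of logic. It takes the criteria of Protocol 13.2.2.2 as written and works through every combination for a subject who has received study drug.

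**Inputs**, each yes or no:
- T: timing is reasonable
- D: the drug could explain the event
- A: an alternative cause is identified
- P: the link is biologically plausible

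An identified alternative is taken to satisfy both the other-causes branch of *related* criterion 2 and the suggested-alternative criterion of *unrelated*.

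**Rules**
- Criterion 2 = D or A or not-A. This is always true, so criterion 2 never decides anything.
- *Related* = T and criterion 2 and P and not-A, which reduces to T and P and not-A.
- *Unrelated* = not-T or A.

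**Results** over 2 × 2 × 2 × 2 = 16 combinations:

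| T | P | A | Combinations | As written | Criterion 4 deleted, nothing else changed |
|---|---|---|---|---|---|
| no | either | either | 8 | unrelated | unrelated |
| yes | yes | no | 2 | related | related |
| yes | yes | yes | 2 | unrelated | meets both definitions |
| yes | no | yes | 2 | unrelated | unrelated |
| yes | no | no | 2 | meets neither | meets neither |

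The counts add up: 8 + 2 + 2 + 2 + 2 = 16.

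**What this shows**
1. As written, 2 of 16 combinations are *related*, and both have no identified alternative. The other-causes phrase in criterion 2 has no effect.
2. Without criterion 4, 4 of 16 meet *related*. The two gained have reasonable timing, plausibility and an identified alternative. One of them is the case at issue, where the drug could also explain the event.
3. In the other gained combination the drug could not explain the event (D = no), yet criterion 2 still lets it through. Deleting criterion 4 alone is therefore not enough.
4. Both gained combinations would still meet *unrelated*, so that definition must change too.
5. Two combinations (reasonable timing, no alternative, no plausibility) fit neither category.

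These are counts of logical cases, not of patients or events. They show the direction of the effect, not its frequency.

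**The case against.** **The criteria can be met together.** A reader might infer that no event can ever be *related*. That is wrong: all four criteria hold when no alternative is identified. The defect is that criterion 4 cancels part of criterion 2.

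**Possible versus identified.** It can be argued that criterion 2 speaks of possible causes and criterion 4 of identified ones, leaving room for an event whose alternative is only suspected. This does not rescue the text. Criterion 2 already has its own branch for no identified alternative, and a merely suggested alternative is enough for *unrelated*. On this reading such an event would satisfy both definitions.

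**Safeguards.** These are real and limit the harm. All SAEs go to the sponsor within 24 hours (13.2.3), and those in the 28-day follow-up are collected whatever the relationship (13.2.2). All adverse events get routine follow-up, and all SAEs are followed to resolution or stability (13.2.2.3). The SAP tabulates treatment-emergent events without regard to relationship (9.2.1, item 1), and does the same for serious events, discontinuations and deaths (9.2.3). A missing rating counts as *related*. None of this corrects an event that has been actively rated *unrelated*.

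**Expedited reporting.** A reader might infer that the investigator's label alone controls it. The documents do not say so. Section 13.2.3 refers to SAEs considered related without saying by whom, and asks for enough detail for an independent causality judgement. An effect there is possible but not shown.

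**Gastrointestinal events.** A reader might expect these to be hit hardest. The documents do not support that either. Protocol 5.2 names them as the most frequent events with this drug, and known association is one of the factors to be weighed, which favours *related*. Inconsistent rating between sites is likewise plausible but a prediction.

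**Conclusion.** The concern holds as a conflict in the wording with a definite direction. As written, an event with reasonable timing, biological plausibility and a possible drug explanation is *unrelated* once another cause is identified, and nothing else in the protocol or SAP resolves this. The clear consequence is under-attribution in the by-relationship tables. Reporting of SAEs after the 28-day period and follow-up to resolution of non-serious events can be narrowed as well.

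The size cannot be computed. If a share q of events that are plausible on timing and biology, and that the drug could explain, also has an identified alternative, then that same share q is rated *unrelated* under a strict reading. The documents give no q, so any percentage would only repeat its own assumption.

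The conclusion assumes that investigators apply the criteria literally; those who follow the spirit of criterion 2 will rate more events as *related*. The primary endpoint, the sample size and the tables that ignore relationship are untouched. The matter should be corrected, but it does not threaten the trial's main result.

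**What to change.** Revise both definitions in Protocol 13.2.2.2 together:
- **Related:** delete criterion 4. Reword criterion 2 to require a reasonable possibility that study drug caused the event, even if other causes are possible. Keep timing and biological plausibility.
- **Unrelated:** remove the suggested-alternative criterion, or narrow it to the existing first criterion, under which the evidence must point clearly to another explanation. Keep the no-drug-received and timing criteria. Adverse events are collected from consent, so pre-dose events need those two.
- **Completeness:** check that every event fits exactly one category. This includes events with reasonable timing, no alternative and no established plausibility, which now fit neither.

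The cost is a short protocol rewording and a site memo. Where events have already been rated, investigators should re-review those marked *unrelated* before database lock. The count of related events may rise. The SAP's two-category tables need no change.

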13.2.2.3. Follow-up of Adverse Events

There should be routine follow-up of AEs in all subjects. Appropriate diagnostic tests should be performed and therapeutic measures, as medically indicated and per standard of care, should be instituted. Appropriate consultation and follow-up evaluations should be carried out.

All SAEs and related AEs will be followed until the event is resolved, clinically stable, or otherwise explained by the Investigator (eg, returned to baseline, is chronic/irreversible).

After the 28-day follow-up period, only unresolved SAEs should be followed at least every 4 weeks until they resolve, improve to baseline level (for “worsening of a pre-existing condition”), or are clinically stable and chronic/irreversible.

Any related SAE occurring after the 28-day follow-up period should be followed at least every 4 weeks until it is resolved, clinical stable, or otherwise explained by the Investigator (eg, has returned to baseline, is chronic/irreversible)

The Medical Monitor or Sponsor may specify a longer period of follow-up time for AEs if required to assure the safety of the subject.

